## 1.4 Treatment / Intervention

Study arm 1: The study arm of 50 patients with benign dry skin conditions will undergo scans with the THz skinometer and will compare the water content of skin before and after application of propriety emollients in common usage (e.g. E45®, Aveeno®, Doublebase®). Participants will have a THz scan of the dry skin area, a control area if possible (similar site but without the skin condition) and a standard reference area (volar forearm with no skin condition present if possible). Then they will apply their emollient and wait 10 minutes to have another scan of the control area and dry skin area. Finally there will be another 10 minute wait before having the final scans of the control area and dry skin area. There will be a minimum of 6 quality scans in total for this group (if the volar forearm is used as the

control area as well as the reference standard). Most likely there will be 7 scans in total (as the reference standard only needs to be measured once)However more scans may be required in order to identify the most suitable area to scan. E.g. if a patient has multiple spots of dry skin on their body, the team may attempt to scan one area but find it is difficult to access and that it does not produce a clear image. In this instance the team would select another dry skin area which is easier to position onto the THz Skinometer. At each time point (pre-emollient and 10 & 20 minutes post emollient) there will be a maximum of 3 scans performed on the dry skin and control area. This is to ensure a meaningful dataset is obtained at each time point.

Study arm 2: The arm with 100 patients with known or suspected skin cancer will have a scan with the THz skinometer in the clinic prior to their planned skin surgery. They will be scanned on the cancerous area, a control area and a reference standard area (the volar forearm) for a minimum of 3 quality scans. In the event that the reference standard and control area are the same, then the participant will only have a minimum of 2 quality scans. The purpose of the reference standard area scan is to act as a calibration point and so we can compare a between subject variable as well as the within subject variable from the cancer/control area. If a participant has multiple potentially cancerous areas on their body, the team will decide which of these areas to scan for the study. If it occurs that the chosen area is too difficult to scan/doesn't produce a clear enough image then a different cancerous area will be selected. There will be a maximum of 3 scans conducted at each of the cancerous area, control area and reference standard area in order to obtain a meaningful dataset. Later the results of the THz scan will be compared to the formal histology results after the primary (melanoma) or residual (BCC) tumour has been removed.

For patients with multiple skin conditions (i.e. multiple dry skin or cancerous locations on the body), we will select the area that is most practical to scan and can make good contact with the scanner.

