For all consenting eligible patients, during the study visit, outcomes will be taken for the affected (area of interest) and unaffected (control) parts of the skin. For each group, a paired t-test will be used to compare the means of outcomes (e.g. skin hydration) for affected and unaffected parts. The corresponding mean difference between affected and unaffected parts and 95% confidence interval (CI) will also be reported. For affected parts, using one way analysis of variance (ANOVA), we will test whether the means for the three groups are equal. Pairwise comparisons using independent t-tests will also be performed, with mean difference and 95% CI reported. We will also compare unaffected parts means for the three groups similarly.

Since this is a feasibility study, we will test all hypotheses at 10% significance level. Also, we will not adjust for multiplicity associated with testing multiple hypotheses. However, for it to be worthwhile conducting a future large study to test utility of THz, clear signals (large differences), estimated using mean differences and 95% CIs, will need to be observed in this feasibility study.

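### The volar forearm may stand in for a site-matched control in both arms, so the affected-versus-control comparisons can mix disease with body site, and Section 8 does not use the forearm scan for its stated calibration purpose

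*Protocol*

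**What the plan says.** **Choice of control.** For arm 1 (benign dry skin), Protocol Section 1.4 asks for "a control area if possible (similar site but without the skin condition" present. It sets a minimum of 6 scans rather than 7 "if the volar forearm is used as the" control as well as the reference. For arm 2 (skin cancer), Section 1.4 states: "They will be scanned on the cancerous area, a control area and a reference standard area (the volar forearm"). It then lowers the minimum from 3 quality scans to 2 "In the event that the reference standard and control area are the same". Section 7.3 repeats both minimums and describes the arm 2 control only as unaffected skin, with no matching to the lesion site.

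**Purpose of the forearm scan.** Section 1.4 says it is there to "act as a calibration point and so we can compare a between subject variable", alongside the within-subject comparison of cancer and control areas.

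**Analysis.** Section 8 takes outcomes from the area of interest and the control area. In each group "a paired t-test will be used to compare the means of outcomes (e.g. skin hydration) for affected and unaffected parts". Affected skin is compared across the three groups by one-way ANOVA and pairwise t-tests, and then: "We will also compare unaffected parts means for the three groups similarly". The reference scan is not named, and nothing in the section separates types of control.

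**What is recorded.** Section 7.2 records the location of the area to be scanned. Section 8.2.1 uses that item to study recruitment. No section asks whether the control was site-matched.

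**The concern.** Pairing removes what is constant within a person. It does not remove a difference between two body sites on that person. If the control is the forearm and the lesion is elsewhere, the paired difference is the disease effect plus whatever separates the two sites. Section 8 puts such differences into the same mean as those from participants with a similar-site control.

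The comparison of unaffected skin has the same weakness: it sets forearm skin in some participants against skin near the lesion in others. If groups differ in how often the forearm is used, that difference enters the group contrast.

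The one reading taken at the same site in everyone is the forearm scan. Section 1.4 gives it a between-subject purpose, but the between-subject tests in Section 8 leave it out.

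At stake is how the hydration results are read. Section 8 says a future large study is worthwhile only if large differences, judged from mean differences and 95% confidence intervals, are seen here. A site effect could create or hide part of such a difference.

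**Working it through.** **The plan's own figure.** Section 8.1 gives 80% power for an independent t-test with 50 per group, a standardised difference of 0.5 and a 10% level. The noncentrality is 0.5 × √(50/2) = 2.5. The two-sided 10% test then has power 80.4% (normal approximation) or 79.9% (noncentral t, 98 df). The figure reproduces and is not disputed. The 0.5 serves below only as a yardstick.

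**Paired comparison.** For one participant:

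- affected reading = person + lesion site + disease
- control reading = person + control site
- difference = disease + (lesion site − control site)

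The second term is taken as zero for a site-matched control. Averaged over a group:

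bias = share with an unmatched control × mean site difference among them.

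The documents give neither factor. The values below are assumptions, with the site difference in SDs of the paired difference:

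| Share | Site difference | Bias |
|---|---|---|
| 10% | 0.5 | 0.05 |
| 25% | 0.5 | 0.125 |
| 50% | 0.5 | 0.25 |
| 10% | 1.0 | 0.10 |
| 50% | 1.0 | 0.50 |

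Two yardsticks help. The planning effect of 0.5 is in between-subject SDs. The SD of a paired difference is √(2(1 − r)) between-subject SDs, which equals 1 at within-person correlation r = 0.5, so the scales coincide only there. With n = 50 the 95% interval for the paired mean has a half-width of about 2.01/√50 = 0.28 SD. A bias of 0.05 is small against that; a bias of 0.25 is nearly as large as the half-width.

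**Effect on the 10% test.** Under no disease effect (simulation, n = 50, two-sided, 20,000 runs), the rejection rate over site differences of 0.25 to 1.0 SD is 11–17% at a 10% share, 13–45% at 25% and 22–95% at 50%. At a 10% share and 0.5 SD it is about 12%, close to nominal. These rates assume that every unmatched control is offset in the same direction.

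**Comparison of unaffected skin.** If the forearm differs from the other control sites by a common amount s, the bias between two groups is (share in A − share in B) × s. With shares of 10% and 50% and s = 0.5 SD, it is 0.4 × 0.5 = 0.20 SD (rejection rate about 25%). With equal shares it is zero, and the rejection rate does not exceed 10%.

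**Use of the forearm scan.** Section 1.4 lists three areas and says what the third is for. Section 8 lists two. The schedule of events for the dry-skin group places the reference scan before emollient, so a pre-emollient forearm reading is planned for every participant in both arms, including those whose forearm is also the control.

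**The case against.** Several stronger readings are tempting, and the documents do not support them.

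- **That the forearm is used whatever the lesion site.** Section 1.4 only provides for control and reference being the same. That includes a lesion on the forearm, where the forearm is the similar site and no bias arises.
- **That substitution is common.** A separate control scan is the stated norm: typically 7 and 3 scans in the participant flow chart notes, and most likely 7 and 3 in Section 7.3. A share of 25–50% has no source in the documents.
- **That a particular false-positive rate follows.** The rates depend on an assumed share and on offsets in one direction. Lesions at varied sites could differ from the forearm in opposite directions. The offsets would then partly cancel and mainly add variance. Section 8 also bases the decision on a further study on mean differences and intervals, not on rejection at 10%.
- **That the forearm scan is never analysed.** When it doubles as the control, it enters as the control. What is missing is its stated calibration use. A separate statistical analysis plan might supply this, but Section 8 already names the tests and the areas that enter them, and following it as written leaves the reference reading out.
- **That the paired analysis should be restricted to site-matched participants.** Arm 2 has no definition of matched. Restriction might also drop people with no similar unaffected skin, perhaps those with more extensive disease.

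These objections limit the size of the point. They do not answer the pooling of unlike controls or the unused purpose of the forearm scan.

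**Conclusion.** The point holds as a design and analysis weakness of unknown size. The protocol permits a forearm control in both arms, requires no site matching in arm 2, and pools all controls as unaffected skin. Where the forearm controls for a lesion elsewhere, the comparison mixes disease with body site. The between-subject use that Section 1.4 gives the forearm scan is not carried into the tests in Section 8.

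The bias equals the share of unmatched controls times their mean site difference, and the documents give neither. If substitution is as infrequent as the stated norm suggests, the bias may be small. At a 50% share and 0.5 SD it would be half the planning effect, taking r = 0.5.

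The feasibility endpoints in Section 3.3, the sample size and the power statement are untouched. What is affected is the secondary hydration comparisons and the judgement on a larger study that rests on them. The correction is cheap enough to make even though the size is unknown.

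**What to change.** 1. **Use the forearm reading for its stated purpose.** In the between-group comparison of affected skin, adjust for the pre-emollient volar forearm reading. Use the same reading for the between-group comparison of unaffected skin, and flag arm 1 participants whose forearm is itself affected, since Section 1.4 makes it condition-free only where possible. The adjustment accounts for differences between people. It does not remove differences in lesion site between groups.
2. **Define and record the control.** In both arms, define it as unaffected skin at a similar body site where possible. Record its location and whether it is site-matched. A forearm control for a forearm lesion counts as matched.
3. **Keep the paired t-test in all participants** and add a sensitivity analysis restricted to those with site-matched controls. Report how many in each group had an unmatched control, so that the share is known.

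**Cost:** one added case report form field and one added analysis per group, with no extra scan beyond those planned. The restricted analysis has fewer participants and so wider intervals.

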## 1.5 Pre-clinical data

In vivo THz images from a case study of patients with BCC in 2004 [1] suggested that it should be possible to detect skin cancer hidden beneath the skin using THz imaging. Spectroscopic studies by [name] (EM; Co-investigator) and her colleagues in Cambridge in 2006 showed that the fundamental THz properties of freshly removed (excised) skin cancer tumours are statistically significantly different from healthy tissue [2] and it is thought that the differences are primarily due to changes in water content of the tissue. The high sensitivity of THz light to water also means that the THz signal is strongly attenuated and has a very limited penetration depth in tissue [3] – thus THz scanning would experience great difficulty in detecting deep tumours. The penetration depth depends on the signal-to-noise ratio of the THz imaging system, therefore efforts to improve the signal processing and/or the THz instrumentation have been made. Since then, EM has been investigating the underlying THz image contrast mechanisms [4,5] as well as developing new algorithms and approaches to improve the accuracy of sample characterisation [6,7] as well as accelerating THz image data acquisition. This more recent work is pushing the state-of-the-art in THz in vivo imaging, both in accuracy and speed. This, crucially, means we are now

better equipped to do THz imaging in vivo studies and we have even been able to account for the pores of skin being blocked (occluded) by the imaging window for the duration of the THz measurement. This 'occlusion' process means the skin cannot breathe normally and water accumulates in the outer most layer of skin, the stratum corneum (SC) [8]. EM has exploited this phenomenon to pioneer the use of THz imaging to determine rate of water diffusion within the SC during occlusion. EM has also been developing in vivo imaging instrumentation techniques and identifying the key variables and parameters such as contact pressure and occlusion duration [9]. EM's latest results show that the refractive index of the skin increases both with increasing pressure and increasing occlusion time. These results will be used to develop the THz skinometer and accompanying characterization algorithms, within this study. EM's findings show how THz imaging can be used to measure the hydration profile and water diffusivity of skin and this is the basis of the theory that will be further developed in the SINATRA study to evaluate the penetration and durability of emollients and sunscreens in different skin types. The pilot data collected in the SINATRA trial will be valuable in developing a larger trial leading to a transformative improvement in prevention and treatment of skin cancer and better moisturisation strategies for other skin conditions.

#### 1.6 Clinical data

There is limited clinical data available due to the novelty of this imaging modality. This data includes a single case study report investigating scarred tissue [5] and a study of five *in vivo* basal cell carcinoma (BCC) skin cancers [1]. Good contrast was seen between normal tissue and regions of tumor in terahertz pulsed imaging of BCC. These changes are consistent with higher water content. These results account for the contrast seen in terahertz images of BCC and explain why parameters relating to the reflected terahertz pulse provide information about the lateral spread of the tumor. No adverse effects were recorded.

## 2. RATIONALE

# 2.1 Aims and hypothesis

The primary aim of SINATRA study is to explore the feasibility of trial methodology

Justification:

The SINATRA trial is an observational study utilising a novel technology thus it is prudent that we collect feasibility data which can inform the development of a definitive trial. We hope that this novel technology, if proven effective, may allow the assessment of emollients and may lead to personalised medicine for the treatment of dry skin conditions. There is also no objective and accepted way to diagnose skin cancer *in vivo* (without biopsy). Current methods are subjective and require training and experience to improve accuracy (clinical examination and dermoscopy). This can result in unnecessary biopsy of benign lesions increasing the risk of patient harm and healthcare costs.

The risk to the patient who is having the scan with the Terahertz (THz) skinometer is negligible. It uses non-ionising radiation, at lower energy that visible light. There is a risk of skin reaction when an emollient is applied. To mitigate this risk, participants will be requested to use emollients they have used previously and they will be requested to bring their own moisturising cream. The scan time is short and painless. The skin area of interest will be placed on the scanner at low pressure. The scanner will be cleaned with standardised clinical cleaning agents between patients. There will be no additional risk compared to standard practice. Patients will be treated in accordance with institutional coronavirus (COVID-19) clinical risk assessments and practice.

## 3. OBJECTIVES AND OUTCOME MEASURES/ENDPOINTS

## 3.1 Primary objective

The primary objective will be to explore the feasibility, test recruitment, trial procedures and refine intervention delivery.

## 3.2 1. Secondary objectives

- To explore if Terahertz skinometry can quantify skin hydration and will show an increase in skin water content after application of an emollient in dry skin conditions.
- To explore if Terahertz skinometry can quantify skin hydration and may indicate the presence of residual basal cell carcinoma after primary excision, or the localised inflammation caused by melanoma skin cancer.

## 3.3 Primary endpoint/outcome

## Feasibility outcomes measures:

- Number of patients screened, eligible, recruited, withdrawn and retained
- Willingness of participants to participate in the trial

## 3.4 Secondary endpoints/outcomes

**Physiological and clinical outcomes**: The secondary outcome is an objective difference in skin hydration between normal skin, benign skin conditions, skin containing residual basal cell carcinoma and skin containing malignant melanoma. The secondary research end point will be after the comparison of scan data with formal reported histological analysis as part of the standard skin cancer management pathway.

#### 4. STUDY DESIGN

A pragmatic, non-randomised, single-centre, feasibility study

#### 5. STUDY SETTING

The SINATRA study will be run within the Department of Dermatology, University Hospitals Coventry and Warwickshire NHS Trust.

Prospective participants will include UHCW staff members and patients suffering from dry skin conditions and known and suspected skin cancer. The patients will be recruited from scheduled Dermatology out-patient clinics including routine general Dermatology clinics (study arm 1: dry skin conditions), two week wait (2WW) urgent Dermatology clinics for suspected skin cancer, and joint clinics run between Dermatology and Plastic Surgery (study arm 2: known or suspected skin cancer). UHCW staff members will be recruited via posters which will be displayed within UHCW and circulated to all staff in internal news bulletins.

The patients will be identified screened and recruited by delegated research team member (Dermatologists, Plastic surgeons, Research Nurse), and scanned with the THz skinometer by non-clinical scientists (Physicists), within a designated clinical area. All non-clinical scientists will have honorary contracts at UHCW, be on the delegation log and have up to date GCP training.

#### 6. ELIGIBILITY CRITERIA

Prospective participants are eligible to participate in the trial if they meet the following criteria

## 6.1 Inclusion criteria

# Study arm 1 (benign dry skin condition) - patients or NHS staff:

- Aged 18 years and over
- Diagnosed with dry skin conditions (e.g. eczema, psoriasis, scars etc.)
- Capacity to give informed consent

## Study arm 2 - patients only:

- Aged 18 years and over
- Confirmed or suspected skin cancer (incompletely excised BCC with histologically proven radial margin involvement, biopsy proven BCC or pigmented lesions suspicious of malignant melanoma).
- Diagnosed with an incompletely excised basal cell carcinoma skin cancer (either radial margin involvement on primary excision or following diagnostic punch biopsy).

- Clinically suspicious pigmented skin lesion (suspected melanoma) with a plan for surgical biopsy
- Capacity to give informed consent

## 6.2 Exclusion criteria

Study Arm 1 (benign dry skin condition)

• Previous allergy or sensitivity to propriety emollients in common usage (e.g. E45®, Aveeno®, Doublebase®etc.).

## 7. TRIAL PROCEDURES

#### 7.1 Recruitment

Prospective participants will be recruited from scheduled Dermatology out-patient clinics including routine general Dermatology clinics (dry skin conditions), two-week wait (2WW) urgent Dermatology clinics for suspected skin cancer, and joint clinics run between Dermatology and Plastic Surgery. Eligible UHCW NHS Trust employees will also be able to participate in the trial in arm 1 only.

Prospective participants who fulfil the inclusion criteria will be invited to participate in the SINATRA study following their consultation, either by a member of the clinical team or the clinical research team. Initial approach and consultation can happen either before a patients clinic visit or on the day of their visit if contact cannot be made beforehand. Patients will not be randomised as part of this pilot feasibility study.

## 7.1.1 Patient identification and Screening

Prospective participants will be identified and screened by a member of their direct healthcare team at the time of clinical review or prior to clinical review from referral letters or photographs. As part of screening following data will be collected for all patients who are invited to be part of the study, including those who decline entry to the study:

- patient hospital ID number
- Basic demographical data

Considering the efforts in the Trust to reduce the number of non-urgent patient visits due to the ongoing pandemic. We will endeavor to contact prospective participants either by telephone or email before their scheduled visit to the dermatology clinic to introduce them to the trial. If they are interested in finding out more they will be referred to a member of the study team, who will explain the study and provide the patient with the PIS and invitation letter following which a delegated member of the research team will confirm their eligibility. If the research team cannot contact the patient before their clinic visit, then a delegated member of the research team can approach them on the day of their visit to first introduce them to the study and offer them an invitation letter and PIS. Following this consultation and after the patient has had a suitable amount of time to consider the trial, they can be invited to enter the study and consent can be taken. In addition study posters

placed around UHCW will inform prospective participants (patients & staff members) about the ongoing trial.

